8.2 SAFETY ASSESSMENTS

No safety assessment were administered.

8.3 ADVERSE EVENTS AND SERIOUS ADVERSE EVENTS

8.3.1 DEFINITION OF ADVERSE EVENTS

An adverse event is defined as any untoward medical occurrence associated with the use of the EMA system.

8.3.2 DEFINITION OF SERIOUS ADVERSE EVENTS

A serious adverse event is defined as any untoward medical occurrence in a clinical trial participant that meets at least one of the following criteria: death, life-threatening injury, results in hospitalization and/or permanent injury.

8.3.3 CLASSIFICATION OF AN ADVERSE EVENT

Please see below.

8.3.3.1 SEVERITY OF EVENT

For adverse events (AEs) not included in the protocol defined grading system, the following guidelines will be used to describe severity.

- (1) Mild: Events require minimal or no treatment and do not interfere with the participants' daily activities.
- (2) Moderate: Events result in a low level of inconvenience or concern with the EMA measures. Moderate events may cause some interference with functioning.
- (3) Severe: Events interrupt a participant's usual daily activity and may require treatment. Severe events are potentially life-threatening or incapacitating.

8.3.3.2 RELATIONSHIP TO STUDY INTERVENTION/EXPERIMENTAL MANIPULATION

All adverse events (AEs) will have their relationship to study procedures, including EMAs, assessed by an appropriately-trained lab member based on temporal relationship and their judgment. The degree of certainty about causality will be graded using the categories below.

- Related: The AE is known to occur with the study procedures, there is a reasonable possibility that the study procedures caused the AE, or there is a temporal relationship between the study procedures and the event. Reasonable possibility means that there is evidence to suggest a causal relationship between the study procedures and the AE.
- -Not Related: There is not a reasonable possibility that the study procedures caused the event, there is no temporal relationship between the study procedures and event onset, or an alternate etiology has been established.

8.3.3.3 EXPECTEDNESS

A trained lab member with appropriate expertise in will be responsible for determining whether an adverse event (AE) is expected or unexpected. An AE will be considered unexpected if the nature,

severity, or frequency of the event is not consistent with the risk information previously described for the study procedures.

8.3.5 ADVERSE EVENT REPORTING

In consultation with the PI, a trained member of the study team will be responsible for conducting an evaluation of a serious adverse event and will report the results of such evaluation to the Tufts CTSI program director, NCATS, and the reviewing Institutional Review Board (IRB) as soon as possible, but in no event later than 7 working days after the investigator first learns of the event.

8.3.7 REPORTING EVENTS TO PARTICIPANTS

Participants will be informed of any significant adverse events (AEs) or serious adverse events (SAEs) that may impact their safety or participation in the study. If an AE occurs, study staff will assess the

Version 1.000

Protocol 15 March 2022

severity, provide appropriate medical guidance, and, if necessary, refer the participant for further medical care. Serious adverse events will be reported to the study's principal investigator, institutional review board (IRB), and relevant regulatory authorities in accordance with established guidelines. Participants will be notified of any changes to study procedures or risks based on reported events. Contact information for reporting concerns or symptoms is provided in the informed consent document.

8.3.8 EVENTS OF SPECIAL INTEREST

N/A

8.3.9 REPORTING OF PREGNANCY

N/A

8.4 UNANTICIPATED PROBLEMS

8.4.1 DEFINITION OF UNANTICIPATED PROBLEMS

This protocol uses the definition of Unanticipated Problems as defined by the Office for Human Research Protections (OHRP). OHRP considers unanticipated problems involving risks to participants or others to include, in general, any incident, experience, or outcome that meets all of the following criteria:

- Unexpected in terms of nature, severity, or frequency given (a) the research procedures that are
 described in the protocol-related documents, such as the Institutional Review Board (IRB)-approved
 research protocol and informed consent document; and (b) the characteristics of the participant
 population being studied;
- Related or possibly related to participation in the research ("possibly related" means there is a reasonable
 possibility that the incident, experience, or outcome may have been caused by the procedures involved in
 the research); and
- Suggests that the research places participants or others at a greater risk of harm (including physical, psychological, economic, or social harm) than was previously known or recognized.

8.4.2 UNANTICIPATED PROBLEMS REPORTING

The investigator will report unanticipated problems (UPs) to the reviewing Institutional Review Board (IRB) and to the principal investigators (PIs). The UP report will include the following information:

- Protocol identifying information: protocol title and number, PI's name, and the IRB project number
- A detailed description of the event, incident, experience, or outcome

Version 1.000

Protocol 15 March 2022

- An explanation of the basis for determining that the event, incident, experience, or outcome represents an UP
- A description of any changes to the protocol or other corrective actions that have been taken or are proposed in response to the UP.

To satisfy the requirement for prompt reporting, UPs will be reported using the following timeline: UPs that are serious adverse events (SAEs) will be reported to the IRB and to the DCC/study sponsor/funding agency within [insert timeline in accordance with policy] of the investigator becoming aware of the event. Any other UP will be reported to the IRB and to the study sponsor within 10 days of the investigator becoming aware of the problem. All UPs will be reported to appropriate institutional officials (as required by an institution's written reporting procedures), the supporting agency head (or designee), and the Office for Human Research Protections (OHRP) within 30 days of the IRB's receipt of the report of the problem from the investigator.

8.4.3 REPORTING UNANTICIPATED PROBLEMS TO PARTICIPANTS

If participant notification is required, the research team will develop a clear, participant-friendly communication that provides a description of the issue, outlines any potential risks, and explains how it may impact participants. The communication will avoid unnecessary alarm while ensuring transparency. Additionally, participants will be informed of any changes to study procedures or additional precautions being implemented to ensure their safety. The notification will also include contact information for participants to reach the study team if they have questions or concerns. Before distribution, the IRB will review and approve the communication to ensure clarity, accuracy, and compliance with ethical guidelines. Participants will be informed through the most appropriate method based on the urgency and nature of the issue. Urgent matters affecting participant safety will be communicated via phone calls to ensure immediate awareness and response. Non-urgent updates, including general study-related changes, will be conveyed through email or mailed letters. In cases where participants are scheduled for in-person study visits, the research team may provide information and discuss concerns during these visits. Regardless of the method used, all communications will be documented in study records to ensure accountability and compliance with study protocols.

9 STATISTICAL CONSIDERATIONS

9.1 STATISTICAL HYPOTHESES

- Primary Efficacy Endpoint(s): Compliance and completion will be significantly higher for participants who complete the 1-item EMA condition versus participants who complete the 9-item EMA condition.
- Secondary Efficacy Endpoint(s): Speech intelligibility will be over 80% across trials. Perceived burden will not significantly differ between participants who complete the 1-item versus 9-item EMA conditions.

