1 PROTOCOL SUMMARY

1.1 SYNOPSIS

Title: Word Retrieval in the Wild: An Ecological Momentary

Assessment Pilot Study in People with Post-Stroke Aphasia

Grant Number: UL1 TR002544

Study Description: People with post-stroke aphasia (PWA) suffer from anomia, a condition

where they know what they want to

say but cannot retrieve the words. For PWA, word retrieval changes

moment-to-moment, leading to diminished

motivation to participate in conversations and disengagement from

social interactions. In the real world, anomia

variability and severity are compounded by contextual factors of

communication exchanges (noise, dual-tasking).

Ecological momentary assessment (EMA) involves in-situ measurement

of a behavior over time during everyday

life. EMA has promise for capturing real-world anomia, yet EMA

methods have not been tested in PWA.

To target in-situ anomia, PWA will complete 36 picture-naming

trials/day for three weeks,

delivered either as a single trial 36 times per day (1-item EMA condition) or in four sets of nine trials/set per day (9-item EMA condition). Prior to completing community/home-based EMAs, participants will undergo standardized testing and smart device training. During the EMA period, participants will complete a brief survey about their EMA experiences at the end of each week. Following completion of the EMA protocol, participants will complete one final

assessment and exit interview session.

Objectives*: Primary Objective: To evaluate the feasibility of ecological

momentary assessment (EMA) of naming abilities in people with post-stroke aphasia

Secondary Determine relationships between feasibility

Objectives: metrics and personal factors

Endpoints*: Primary Endpoint: Compliance and completion over a 3-week

EMA protocol

Secondary Perceived burden of completing EMAs

Endpoints: during the 3-week protocol

Study Population: Individuals with post-stroke aphasia

Phase* or Stage: Chronic stroke (at least 6 months after stroke onset)

Description of Sites/Facilities Enrolling Participants:

Participants will be recruited through The Aphasia Network (TAN) Lab at Northeastern University.

[figure not shown]
Description of Study Manipulation:

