2.2 BACKGROUND

Impaired word retrieval—also known as anomia—is one of the most debilitating symptoms stroke survivors with aphasia, a communication disorder characterized by impaired language, face in their daily lives. Like "tip-of- the-tongue" states experienced by neurotypical individuals, anomic moments in people with aphasia (PWA) occur when an individual knows what they want to say but cannot retrieve the word. Unlike "tip-of-the-tongue," anomia in PWA pervades communication exchanges and is characterized by inconsistent ability to retrieve a given word across attempts. The severity and unpredictability of anomia lead many PWA to disengage from conversation and social situations, which can severely impact their participation and quality of life. In daily life, anomia can be further compounded by real-world communication contexts such as attempting to communicate in distracting settings (e.g., with background noise and/or other people in the vicinity) or when completing other tasks. In clinical practice, speech-language pathologists (SLPs) typically assess anomia by administering a standardized test once to a patient in a quiet room. This approach captures neither the variability typical of post-stroke anomia nor the realities of real-world communication. In contrast, ecological momentary assessment (EMA) is a method often used in health research to measure physical, mental, or cognitive states in a person's daily life over several days, weeks or even months. Traditional EMA involves a device prompting a participant to answer a set of questions a few times a day, whereas micro-interactionbased EMA (µEMA) uses single-question, "at-a-glance" prompts that are interspersed over time rather than grouped into sets. Our pilot studies demonstrate that µEMA has higher response rates and lower perceived burden than traditional EMA in neurotypical individuals despite its higher interruption rate. Thus, we propose that EMA—particularly µEMA—is a viable approach to capture real-world anomia in PWAs' daily lives. Yet, despite the increasing use of technology-based assessments and therapy platforms for PWA, neither EMA nor µEMA methods have been utilized in aphasia.

Version 1.000

Protocol 15 March 2022

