4.2 SCIENTIFIC RATIONALE FOR STUDY DESIGN

The study design will allow the research team to address the primary objectives of assessing protocol feasibility in multiple ways (compliance, completion, and perceived burden) as well as the secondary objective of exploring personal factors (age, cognitive abilities) that relate to feasibility metrics.

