9.2 SAMPLE SIZE DETERMINATION

For the Aim #1 logistic mixed effects models, two groups of 10 PWA per group will achieve 80% power to detect an odds ratio of 1.20 in a design of 756 repeated measures with a AR(1) covariance structure and when the correlation between observations of the same subject is 0.600 and alpha is 0.05. If the proportion of completed trials for the EMA group is 0.500, a statistically significant result will occur if the μ EMA group proportion is 0.545 or greater. In [name] et al.4, the mean difference in proportions between the μ EMA and EMA conditions was >0.20 for compliance and completion, which is much higher than the needed 0.045 difference. This suggests we will have ample power to detect significant differences between the two conditions.

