9.4.3 ANALYSIS OF THE SECONDARY ENDPOINT(S)

Every audio clip (n trials will vary by person, depending on the number of naming attempts) will be coded as 0 for completely or partially unintelligible and 1 for completely intelligible, reflecting speech intelligibility. We will run a logistic mixed effects model with intelligibility as the dependent variable, condition (1-item vs. 9-item) as the independent variable, and random effects of participant and trial. For perceived burden, we will collect responses on three questions/survey for three weeks. Given the small amount of data, survey responses will be plotted to visualize trends in increasing/decreasing burden rather than compared statistically. We will statistically compared averaged burden ratings between participants in the 1-item vs. 9-item condition using t-tests or Wilcoxon rank sum tests (depending on the distribution of the data).

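### The burden hypothesis predicts non-significance, so a weak 10-versus-10 test makes it easier to meet, and no interval is planned to show what the data rule out

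*Combined protocol and SAP*

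**What the plan says.** Section 9.1 lists, as a hypothesis for a secondary endpoint, "Perceived burden will not significantly differ between participants who complete the 1-item versus 9-item EMA conditions".

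Section 9.4.3 describes the data, "we will collect responses on three questions/survey for three weeks", and averages the ratings. It sets statistical testing aside for change over the weeks: "survey responses will be plotted to visualize trends in increasing/decreasing burden rather than compared statistically". It still compares the two conditions on the averaged ratings, "using t-tests or Wilcoxon rank sum tests (depending on the distribution of the data"). It gives no interval for the difference, no margin, and no rule for reading a non-significant result.

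Section 6.1.1 assigns 10 participants to each condition. The only sample size statement, in section 9.2, is limited to other endpoints: "For the Aim #1 logistic mixed effects models, two groups of 10 PWA per group will achieve 80% power".

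**The concern.** A significance test can reject equality but cannot confirm it. When non-significance is itself the predicted result, the usual incentive is reversed: fewer participants, noisier ratings or more dropout all raise the chance that the prediction comes true. A supported hypothesis would then not separate similar burden from too little information.

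This matters here for three reasons.

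- The synopsis names "Perceived burden of completing EMAs" as its only secondary endpoint.
- Section 4.2 counts burden among the ways of "assessing protocol feasibility in multiple ways (compliance, completion, and perceived burden").
- Section 2.2 says that in the team's own pilot work single-item prompting "has higher response rates and lower perceived burden than traditional EMA in neurotypical individuals despite its higher interruption rate". On the plan's own evidence, a real difference between conditions is plausible.

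**Working it through.** **Inputs.** 10 per condition (6.1.1). Three questions in each of three weekly surveys, so 3 × 3 = 9 ratings per participant, averaged to one value (section 3, 9.4.3); the test sees 20 values in all. Assumptions: alpha 0.05, which 9.2 states only for the Aim 1 models; a two-sided test, because the hypothesis is non-directional; and effects in SD units, because no SD for burden is given.

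**The plan's own power figure.** With AR(1) correlation 0.6 over 756 trials, the design effect is 1 + 2 Σ(1 − k/756)·0.6^k = 3.99. Effective trials per arm are 10 × 756 / 3.99 ≈ 1,895. An odds ratio of 1.20 from 0.500 gives 0.545. The standard error of the log odds ratio is √[1/(1,895 × 0.5455 × 0.4545) + 1/(1,895 × 0.25)] ≈ 0.065. Then ln(1.20)/0.065 ≈ 2.80, and 2.80 − 1.96 = 0.84, which is 80% power. The figure reproduces, but it rests on 756 trials per person. Burden contributes one value per person.

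**Boundary for the burden t-test.** t(0.975, 18) × √(1/10 + 1/10) = 2.101 × 0.447 = 0.940 observed pooled SD. A smaller observed difference gives p > 0.05. The same quantity is the half-width of the 95% CI. It is 1.00 with 9 per arm and 1.07 with 8 per arm. If the test were one-sided at 0.05, it would be 0.78 with 10 per arm.

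**Chance that the hypothesis is met.** For the t-test: noncentral t, 18 df, noncentrality d√(10/2). For Wilcoxon: exact cut-offs U ≤ 23 or U ≥ 77 (exact size 0.043), normal data, 40,000 simulations.

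| True difference (SD) | t-test power | Hypothesis met, t-test | Wilcoxon power | Hypothesis met, Wilcoxon |
|---|---|---|---|---|
| 0 | 5% | 95% | 4.3% | 95.7% |
| 0.5 | 18.5% | 81.5% | 16.3% | 83.7% |
| 0.8 | 39.5% | 60.5% | 35.2% | 64.8% |
| 1.0 | 56.2% | 43.8% | 51.3% | 48.7% |

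The t-test reaches 80% power only at a true difference of 1.32 SD. If two per arm were lost (an assumption), its power at 0.8 SD would fall to 32%.

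**How far 0.94 applies to Wilcoxon.** It is exact only for the equal-variance t-test. In simulation at true differences of 0.5 to 1.0 SD, about 1–2% of datasets were significant by Wilcoxon below 0.94 and about 4–7% were non-significant above it. It is a fair guide, not a cut-off.

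**Would an equivalence test serve instead?** With no true difference and 10 per arm, the 90% CI rule succeeds about 12% of the time at a margin of ±0.8 SD and 39% at ±1.0 SD (margins assumed). For 80% success it needs about 28 and 18 per arm.

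**The case against.** The strongest reply is that nothing follows from this test. Section 9.1 is a prediction, and no passage attaches a go/no-go rule, a claim or a design choice to the burden comparison. Section 3 states the burden objective without a comparison, so the level of burden can be described whatever the test shows. Section 4.4 calls the study a small-scale feasibility trial, where low power on a secondary endpoint is expected. Section 9.4.8 plans participant-level listings by measure; if burden is among them, a reader could compute the difference and its interval.

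Most of this stands, and it limits the point. Two stronger readings are tempting, and the documents support neither.

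- A reader might infer that the investigators will report p > 0.05 as equivalence. No passage says so.
- A reader might infer that the data will leave similar burden and too few participants indistinguishable. The listings, if they include burden, and the weekly plots would give a reader something to work with.

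The reply does not remove the fault in the stated hypothesis, which is met by non-significance whatever the reason for it. A listing from which an interval might be rebuilt does not replace a planned one. Nor is low power the complaint: a pilot need not be powered for burden, and its small size argues for estimating the difference.

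**Conclusion.** The point holds as a fault of inference and reporting on a secondary endpoint. The burden hypothesis is met by any non-significant result, with no interval or margin to show which differences remain compatible with the data. At 10 per arm and an assumed two-sided 0.05, a true 0.8 SD difference in either direction meets it about 60% of the time by t-test and about 65% by Wilcoxon.

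The 0.94 boundary is in observed pooled SD units and belongs to the t-test. It should not be read as a limit for both planned tests, and it cannot be put in Likert points without an SD for burden. The Wilcoxon figures also assume normal data. Since no decision hangs on the test, the primary analyses are unaffected.

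**What to change.** 1. In 9.1, replace the burden hypothesis with an estimation aim, for example: *We will estimate the difference in averaged perceived burden between conditions, with a 95% confidence interval.*
2. In 9.4.3, add that the difference (1-item minus 9-item) in averaged ratings will be reported with a 95% CI, or the Hodges-Lehmann shift with its CI if the Wilcoxon test is used. State the alpha and sidedness of the test.
3. In 9.4.3, add that a non-significant result is inconclusive about similarity.

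Keep the planned test and the weekly plots. Make no equivalence claim at this sample size, given the success rates worked out above.

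The cost is a few sentences and one interval from data already being collected, with no extra participants or visits. The downside is a more guarded conclusion and a wide interval: a half-width of about 0.94 SD for the t-test and a mean of about 0.98 SD for Hodges-Lehmann on simulated normal data.

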9.2 SAMPLE SIZE DETERMINATION

For the Aim #1 logistic mixed effects models, two groups of 10 PWA per group will achieve 80% power to detect an odds ratio of 1.20 in a design of 756 repeated measures with a AR(1) covariance structure and when the correlation between observations of the same subject is 0.600 and alpha is 0.05. If the proportion of completed trials for the EMA group is 0.500, a statistically significant result will occur if the μ EMA group proportion is 0.545 or greater. In [name] et al.4, the mean difference in proportions between the μ EMA and EMA conditions was >0.20 for compliance and completion, which is much higher than the needed 0.045 difference. This suggests we will have ample power to detect significant differences between the two conditions.

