8.1 ENDPOINT AND OTHER NON-SAFETY ASSESSMENTS

Endpoint Assessments: Feasibility will be classified in three ways: (1) PWAs' adherence to the smartwatch μΕΜΑ or EMA protocol via compliance and completion, (2) PWAs' perceived burden of completing the EMA protocol, and (3) speech intelligibility of recorded naming attempts. Currently, PWAs' capacity for adhering to a smartwatch EMA protocol via button press responses or verbal responses is unknown. As such, compliance will be based on the number of YES button responses to the "Ready?" screen whereas completion will be based on naming attempts. Specifically, similar to [name] et al. (2016), compliance will be determined by the number of YES responses over scheduled trials, including trials missed due to the watch being off/uncharged. Completion will be calculated as trials with captured audio (reflecting attempted naming) over delivered trials, excluding trials missed to the watch being off/uncharged. Perceived burden will be measured via responses to the weekly surveys during weeks 2-4. Finally, speech intelligibility will be measured by a categorical rating of responses captured in each audio clip (i.e., completely intelligible, partially intelligible, or completely unintelligible).

Other Non-Safety Assessments: Before the EMA period, PWA will be administered the following testing battery. The Quick Aphasia Battery (QAB) will be used as our eligibility assessment and to measure overall aphasia severity. The Pattern Comparison Processing Speed Test and Flanker Inhibitory Control and Attention Test from the NIH Cognition Toolbox will be used to measure non-linguistic visual attention and executive functions, respectively. We will use brief, standardized picture description and story elicitation tasks from the AphasiaBank protocol to index anomia in discourse. Participants will complete an overt object naming test twice before EMA and once after EMA so that the research team can evaluate word retrieval via the standard SLP assessment format (i.e., single administration in a quiet 1:1 interaction). This picture naming probe will include normed real photos of the 260 items from the Snodgrass and Vanderwart stimuli set. Before EMA, PWA will also participate in an intake interview and complete a questionnaire about their comfort with technology, adapted for aphasia (simple language, short phrases).

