9.4.2 ANALYSIS OF THE PRIMARY ENDPOINT(S)

We will code each trial in the EMA time series to index compliance, completion, and speech intelligibility. Every scheduled trial (n = 756 total trials) will be coded as 0 for a nonresponse/ NO button

Version 1.000

Protocol 15 March 2022

response or 1 for a YES button response, reflecting compliance. Every delivered trial with a naming attempt captured on audio (n trials will vary by person) will be coded as 0 for incomplete or 1 for complete, reflecting completion. For each of these measures, we will run a logistic mixed effects model with one of the feasibility measures (i.e., compliance, completion) as the dependent variable, condition (1-item vs. 9-item) as the independent variable, and random effects of participant and trial.

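### Section 9.2 gives 80% power at an odds ratio of 1.20 for both primary models from 756 scheduled trials, but completion is analysed on delivered trials only, so for completion 80% is an upper limit

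*Combined protocol and SAP*

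**What the plan says.** Section 9.2 makes one power statement for more than one model: "For the Aim #1 logistic mixed effects models, two groups of 10 PWA per group will achieve 80% power". In full, the groups are to "achieve 80% power to detect an odds ratio of 1.20 in a design of 756 repeated measures", with an AR(1) correlation of 0.600 and alpha 0.05. The worked example is framed in terms of completion: "If the proportion of completed trials for the EMA group is 0.500", the other group is to reach 0.545. The section then cites a difference above 0.20 from an earlier study, for both compliance and completion, and concludes that power is ample.

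Section 9.4.2 identifies the models: "we will run a logistic mixed effects model with one of the feasibility measures (i.e., compliance, completion) as the dependent variable". It codes compliance on every scheduled trial, n = 756. Section 6.1.2 derives that count from 36 trials a day over three weeks.

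Completion has a different denominator. Section 8.1: "Completion will be calculated as trials with captured audio (reflecting attempted naming) over delivered trials, excluding trials missed to the watch being off/uncharged". Section 9.4.2 describes the number of completion records with the words "n trials will vary by person) will be coded as 0 for incomplete or 1 for complete". The objectives table in section 3 and the exploratory definitions in 9.4.9 also divide completion by what was delivered.

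No section gives an expected delivered fraction, a second base proportion or a separate power figure for completion.

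**The concern.** The trial count behind the 80% belongs to compliance. For completion 756 is the maximum, reached only if no participant ever has the watch off or uncharged. The plan foresees such losses: 8.1 defines completion so as to exclude them, and 5.3 notes that some participants may have difficulty with tasks such as charging.

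The calculation also rests on a single base proportion. At a fixed odds ratio, 0.500 is close to the value that gives the highest power, so the example shows the favourable end for either endpoint.

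Completion is one of two primary endpoints and carries a superiority hypothesis (9.1). Someone relying on 9.2 could take a non-significant completion result as coming from a comparison with 80% power at an odds ratio of 1.20, when the design gives less than that.

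**Working it through.** **Inputs from 9.2:** 10 per group; m = 756 measures per participant; AR(1) correlation 0.6; alpha 0.05; base p1 = 0.500; odds ratio 1.20. The sidedness of alpha is not stated. Two-sided reproduces the figure, while one-sided gives 87.6%.

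**Step 1: reproduce the 80%.**
- Design effect of a mean of m AR(1) measures: DE = 1 + S, where S = 2 × Σ(1 − k/m) × 0.6^k for k = 1 to m − 1. At m = 756, S = 2.990 and DE = 3.990.
- Effective number per group: 10 × 756 / 3.990 = 1894.7.
- Odds ratio 1.20 on a base of 0.500 gives odds of 1.2 and p2 = 1.2/2.2 = 0.5455.
- SE² = 1/(1894.7 × 0.25) + 1/(1894.7 × 0.5455 × 0.4545), so SE = 0.0651.
- Power = Φ(ln 1.20 / SE − 1.96) = Φ(0.1823/0.0651 − 1.96) = Φ(0.84) = 80.0%.

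The plan's figure is therefore a two-sided AR(1) calculation with all 756 trials observed.

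**Step 2: change only the trial count.** Let f be the delivered fraction, which is **an assumption**. Two patterns of loss bracket the result:
- Blocks (for example, watch off for a stretch): effective n = 10m′/DE(m′), with m′ = 756f.
- Scattered single losses: effective n = 10 × 756f / (1 + f × 2.990), because surviving neighbours lie further apart and are less correlated.

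| f | Effective n, blocks | Power | Effective n, scattered | Power |
|---|---|---|---|---|
| 1.00 | 1895 | 80% | 1895 | 80% |
| 0.95 | 1800 | 78% | 1870 | 79% |
| 0.90 | 1705 | 76% | 1843 | 79% |
| 0.80 | 1517 | 71% | 1783 | 78% |
| 0.60 | 1140 | 58% | 1623 | 74% |

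**Step 3: change only the base proportion** (all 756 trials, so this covers compliance as well).

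| Base | Power at odds ratio 1.20 | Power at a difference of 0.045 |
|---|---|---|
| 0.50 | 80% | 79% |
| 0.70 | 71% | 87% |
| 0.80 | 59% | 95% |
| 0.90 | 37% | >99% |

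Below one half there is no gain at a fixed odds ratio: 79% at base 0.40 and 74% at 0.30. The maximum over all bases is 80.1%, at about 0.47.

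**Step 4: the effect that the plan expects.** At a difference of 0.20 (0.50 against 0.70), power under the same model exceeds 99.9% even with half the trials delivered in blocks (m′ = 378, effective n about 950).

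**The case against.** The strongest reply is that little of practical weight is lost. The plan expects a difference above 0.20, and step 4 shows that its own model still has ample power for completion at that size. With 95% delivery and the base kept at 0.500, power is still 78-79%. Training covers charging (1.3), and missed trials are raised at the weekly check-ins (7.1), so heavy loss is not a given. All of this stands. It limits the importance of the point but does not make the 80% at an odds ratio of 1.20 correct for completion.

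A reader might infer a larger shortfall: if half of scheduled trials are answered, removing undelivered trials lifts the completion base to 0.50/f, and holding the odds ratio at 1.20 then gives 35-78% power for f from 0.60 to 0.90. The documents do not support this. Section 9.2 words its 0.500 as a proportion of completed trials, not of answered scheduled trials. The same division would also apply to the other arm. With equal delivery in both arms, 0.500 and 0.5455 become 0.556 and 0.606 at f = 0.90 (odds ratio 1.23), 0.667 and 0.727 at 0.75 (1.33), and 0.833 and 0.909 at 0.60 (2.00). Power, with losses in blocks, is then about 85%, 94% and over 99%: it rises.

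The base-proportion point is also not a fault of completion alone. It applies equally to compliance, and it reverses if the target is the 0.045 difference that 9.2 also quotes.

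Lastly, every figure here inherits the AR(1) correlation. Section 9.4.2 plans a participant random effect, and with a constant within-participant correlation of 0.6 the design effect is 1 + 755 × 0.6 = 454, with power of about 4-5% at an odds ratio of 1.20. That is a separate and larger question. The figures above correct the statement within 9.2's own model and do not endorse that model.

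**Conclusion.** The point holds in a limited form. On 9.2's own inputs the 80% is right for an outcome observed on all 756 scheduled trials with a base near 0.50. For completion it is an upper limit. The shortfall is one to two percentage points at 95% delivery, one to four at 90%, two to nine at 80% and six to 22 at 60%, depending on whether losses are scattered or in blocks. The actual size is unknown, because no delivered fraction is given.

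For both endpoints, the 80% at a fixed odds ratio of 1.20 also depends on a base near one half.

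It would be going too far to conclude that completion lacks power for the effect the plan expects, or that it should come out of the statement on ample power. That statement rests on the cited difference above 0.20, which this correction does not touch.

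**What to change.** In 9.2:

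- Say that the 80% at an odds ratio of 1.20 applies to an outcome observed on all 756 scheduled trials with a base proportion near 0.50.
- Add a separate line for completion, giving power at an odds ratio of 1.20 over a stated range of delivered fractions (for example 0.60 to 0.95), with the assumed pattern of loss.
- Show power over a range of base proportions (for example 0.5 to 0.9) for both endpoints, and say whether the target effect is the odds ratio or the absolute difference, since the two move in opposite directions.
- Keep completion in the sentence on ample power, but say that it rests on the cited difference above 0.20 and not on 80% at an odds ratio of 1.20.

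The cost is a few lines of text and a slightly less favourable stated figure for completion. No participants or data are added, and the sample size stays the same.
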